5.5 IMPORTANT PROTOCOL DEVIATIONS

An important protocol deviation (IPD) is a deviation that may significantly affect the completeness, accuracy, or reliability of the study data or that may significantly affect a subject's rights, safety, or well-being. IPD rules will be developed and finalized prior to the database lock.

The protocol deviations that should be considered as potential IPDs include, but are not limited to:

[figure not shown]
- Subject was randomized despite the violation of inclusion/exclusion criteria
- Subject was less than 80% compliant with study drug
- Subject received prohibited concomitant medications
- Subject received the wrong treatment or incorrect doses
- Subject remained in the study despite meeting withdrawal criteria

Occurrence of any of these events should be considered as potential IPDs, but a blinded team should categorize them as IPDs only if they have the potential to significantly affect the completeness, accuracy, or reliability of the study data or that may significantly affect a subject's rights, safety, or well-being.

IPDs (from the clinical database or from the site deviation log) will be summarized descriptively based on the FAS and presented by treatment sequence in Part A and by treatment in Part B. Additionally, IPDs will be provided in an individual subject data listing.

1006696
Parion Sciences Incorporated
CLEAN-PCD
SAP Version 1.0

6 GENERAL ASPECTS FOR STATISTICAL ANALYSIS

6.1 GENERAL METHODS

All analyses will be implemented using SAS Version 9.3 or higher. Data summaries will be presented by treatment . All data will be listed.

Continuous variables will be summarized using the following descriptive summary statistics: number of subjects (n), mean, SD, median, minimum value (min), and maximum value (max).

Categorical variables will be summarized using counts and percentages. Percentages will be presented to 1 decimal place.

General rules of precision are as follows:

- Minimum and maximum values will be reported with the same precision as the reported measurement unless otherwise specified. For the calculated variables, two decimal places will be reported.
- Mean and median will be reported to 1 greater decimal place than the precision of the reported measurement unless otherwise specified.
- Standard deviation and standard error (to indicate standard error of an estimate from a statistical model) will be reported to 1 greater decimal place than the corresponding mean.
- Report p-values to 4 decimal places; report as “<0.0001”, when applicable.
- In general, the precision of mean, LS Mean, and 95% CI for a variable is the same, unless otherwise specified.

[figure not shown]
6.2 KEY DEFINITIONS

6.2.1 Baseline

Two types of baseline will be defined for Part A. The **study baseline** is defined as the most recent nonmissing measurement (scheduled or unscheduled) collected before the first dose of study drug in the study. The definition will be applied to all demographics, background, and baseline characteristics and efficacy data analyses, including the primary endpoint analysis. The **period baseline** is defined as the most recent nonmissing measurement (scheduled or unscheduled) collected before the first dose of study drug in each Treatment Period. For Part A Treatment Period 2, the period

1006696
Parion Sciences Incorporated
CLEAN-PCD
SAP Version 1.0

baseline will be the first assessment measured after treatment-emergent (TE) period for Period 1. This definition will be applied to all safety data analyses.

For spirometry analysis in Part A, if Period 1 day 1 pre-dose data is not available, data collected at the screening visit before the test HS dose will be used as Period 1 baseline or study baseline instead of the last non-missing screening visit after the test HS dose.

For weight, height and BMI, study baseline and Period 1 baseline will be defined as the most recent non-missing measurement (scheduled or unscheduled) collected before or on the day of the first dose of study drug in Part A, Period 1. Similarly, Period 2 baseline will consider the most recent non-missing measurement (scheduled or unscheduled) collected after the TE period for Period 1 and before or on the day of first dose of study drug in Part A, Period 2.

For SGRQ and QOL-PCD, study baseline will be defined as the most recent non-missing measurement (scheduled or unscheduled) collected before or on the day of the first dose of study drug in Part A, Period 1.

For Part B, two types of baseline, study baseline and Part B baseline, will be defined. The study baseline is defined the same as study baseline for Part A. The Part B baseline is defined as the most recent non-missing measurement (scheduled or unscheduled) collected before the first dose of ivacaftor in Part B and after the last dose in Period 2.

- Change/Absolute change from study baseline in Part A and Part B will be calculated as:

post-baseline value - study baseline value.

- Change/Absolute change from period baseline in Part A will be calculated as:

post-baseline value - period baseline value.

- Change/Absolute change from Part B Baseline will be calculated as:

post-baseline value - Part B baseline value

[figure not shown]
For weight, height and BMI, SGRQ and QOL-PCD, Part B baseline will be defined as the most recent non-missing measurement (scheduled or unscheduled) collected before or on the day of the first dose of ivacaftor in Part B and after the last dose in Period 2.

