**8.1.3.1.2 Washout Period**

Subjects will undergo a Washout Period of 28 days (+ 3 days) between Treatment Period 1 and Treatment Period 2. Subjects should continue to maintain a consistent medication and airway clearance regimen throughout the Washout Period. The Washout Period may be extended for an additional 28 days for acute upper or lower respiratory infections following discussion and approval of the Parion medical monitor.

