#### **Treatment-emergent Period**

Treatment-Emergent Period for Part A Treatment Period 1:

- For subjects who prematurely discontinue treatment in Part A Treatment Period 1, the Treatment-Emergent Period will be defined as the interval that occurs on or after first dose of Treatment Period 1 and up to 28 days after the last dose in Treatment Period 1.
- For subjects who continue into Treatment Period 2, the treatment emergent period will be defined as the interval that occurs on or after first dose of study drug in Treatment Period 1 and before first dose of study drug in Treatment Period 2.

Treatment-Emergent Period for Part A Treatment Period 2:

- For subjects who prematurely discontinue treatment in Treatment Period 2, the treatment-emergent period will be defined as the interval that occurs on or after first dose of study drug in Treatment Period 2 and up to 28 days after the last dose in Treatment Period 2.
- For subjects who complete Treatment Period 2, the treatment-emergent period will be defined as the interval that occurs on or after first dose of Treatment Period 2 and before first dose of Part B (Treatment Period 3).

Treatment-Emergent Period for Part B Treatment Period 3:

For subjects who receive treatment in Part B, the treatment-emergent period will be defined as the interval that occurs on or after first dose of study drug in Part B until the end of study.

**Baseline:** 2 types of baselines will be defined for Part A. The **study baseline** is defined as the most recent nonmissing measurement (scheduled or unscheduled) collected before the first dose of study drug. The definition will be applied to all demographics, background, and baseline characteristics and also efficacy data analysis, including the primary endpoint analysis. The **period baseline** is defined as the most recent nonmissing measurement (scheduled or unscheduled) collected before the first dose of study drug in each Treatment Period. For Part A Treatment Period 2, the period baseline should be from an assessment measured after the last dose for Treatment Period 1. This definition will be applied to all safety data analysis. This definition will be applied to all safety data analysis in Part A and Part B.

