6.2.2 Treatment Emergent Period

Treatment-emergent (TE) period for Part A Treatment Period 1:

1006696
Parion Sciences Incorporated
CLEAN-PCD
SAP Version 1.0

- The Treatment-Emergent Period will correspond to the interval from the first dose date of Treatment Period 1 to 28 days after the last dose date of Treatment Period 1 or the date before the first dose date of Treatment Period 2 or the safety follow-up visit, whichever occurs earlier.

TE period for Part A Treatment Period 2:

- The treatment emergent period will correspond to the interval from the first dose date of Treatment Period 2 to 28 days after the last dose date of Treatment Period 2 or the date before the first dose date of Part B or the safety follow-up visit, whichever occurs earlier.

Treatment-Emergent Period for Part B:

- The treatment emergent period will correspond to the interval from the first dose date of study drug in Part B to 28 days after the last dose date of Part B or the safety follow-up visit, whichever occurs earlier.

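### SAP 6.2.1 gives two conflicting rules for the Period 2 safety baseline, and after an extended washout they can select different values (minor)

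*SAP*

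**What the plan says.** SAP 6.2.1 starts with a general rule. The period baseline is the "most recent nonmissing measurement (scheduled or unscheduled) collected before the first dose of study drug in each Treatment Period". For Period 2 it then says that the "baseline will be the first assessment measured after treatment-emergent (TE) period for Period 1", and adds: "This definition will be applied to all safety data analyses". For weight, height and BMI the same section goes back to the latest value: "Period 2 baseline will consider the most recent non-missing measurement (scheduled or unscheduled) collected after the TE period for Period 1", up to the day of the first Period 2 dose.

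Protocol 12.3.1 has the same general rule but a looser restriction for Period 2: "the period baseline should be from an assessment measured after the last dose for Treatment Period 1". It does not switch from the latest value to the first.

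The two documents also end the Period 1 TE period differently. For subjects who go on to Period 2, protocol 12.3.1 runs it up to the first Period 2 dose. SAP 6.2.2 ends it at the earliest of several dates, including "28 days after the last dose date of Treatment Period 1 or the date before the first dose date of Treatment Period 2".

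On the length of washout, protocol 8.1.3.1.2 plans 28 days (+3) and adds: "The Washout Period may be extended for an additional 28 days for acute upper or lower respiratory infections". Protocol 8.1.6 allows unscheduled visits. SAP section 11 records no change from the protocol.

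**The concern.** The latest value before dosing and the first value after the TE period are different selection rules. They agree only if nothing is measured between the end of the TE period and the start of Period 2 dosing. Two programmers working from this one paragraph could build different Period 2 baselines.

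The period baseline is the reference for the Part A safety summaries in SAP section 10, and safety and tolerability results are a listed primary endpoint. If a value from a subject still recovering from an infection became the baseline, a later fall on Period 2 drug would be understated. If the early value happened to be better than the pre-dose value, a fall would be overstated. In both cases the table would no longer measure change from the subject's state at the start of Period 2 treatment.

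**Working it through.** **Inputs.** Last Period 1 dose: Day 28 on the morning schedule, Day 29 on the afternoon schedule (protocol 8.1.3.1.1). First Period 2 dose: Day 57 as planned, Day 60 with the +3 days, Day 85 with the 28-day extension (57 + 28), Day 88 with both. TE rule: SAP 6.2.2. The safety follow-up alternative in that rule does not apply to a subject who continues.

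**Check on the plan's own figure.** Washout Day 29 through Day 56 is 56 − 29 + 1 = 28 days, as stated.

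**Formulas.** With L the last Period 1 dose day and F the first Period 2 dose day:

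- TE end = min(L + 28, F − 1)
- Gap = F − 1 − TE end, the days after the TE period and before the Period 2 dosing day

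| L | F | TE end | Gap (days) |
|---|---|---|---|
| 28 | 57 | min(56, 56) = 56 | 0 |
| 29 | 57 | min(57, 56) = 56 | 0 |
| 28 | 60 | min(56, 59) = 56 | 3 |
| 29 | 60 | min(57, 59) = 57 | 2 |
| 28 | 85 | min(56, 84) = 56 | 28 |
| 29 | 85 | min(57, 84) = 57 | 27 |
| 28 | 88 | min(56, 87) = 56 | 31 |
| 29 | 88 | min(57, 87) = 57 | 30 |

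With no gap, the first assessment after the TE period is normally the Day 57 pre-dose value, which is also the latest before dosing. With a gap, any assessment in it comes first and displaces the pre-dose value. The visit windows in SAP Appendix VI start after Day 1 of each period, so they neither choose the Period 2 baseline nor screen out such a value.

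**Who can have an assessment in the gap.** Protocol 8.1.3.1.3 asks for 28 days free of infection, exacerbation or change in pulmonary therapy before the Day 57 Visit, and otherwise refers continuation to the medical monitor. Reading that visit as the actual Period 2 start, a Day 85 start needs a clear interval from Day 57 (85 − 28). That is almost exactly the gap. For a subject who meets the condition, sick visits therefore fall inside the TE period and cannot become the baseline. Three routes remain:

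- a subject who attends around Day 57, is assessed, and is deferred without dosing. With L = 28 a Day 57 value lies in the gap; with L = 29 the TE period ends that day and the value is not eligible;
- an unscheduled follow-up visit during the extension;
- a sick visit in a subject continued after discussion with the medical monitor.

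**Illustration (all measured values assumed).** L = 28. The subject attends Day 57 undosed, with ppFEV1 55 and saturation 93%. Period 2 starts on Day 85, with pre-dose ppFEV1 64 and saturation 97%. At the end of Period 2 ppFEV1 is 54, and the lowest saturation is 94%.

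- First-assessment rule: 54 − 55 = −1 point. Saturation is low at baseline (SAP 10.7 counts ≤95% as low), so there is no normal-to-low shift.
- Latest-value rule: 54 − 64 = −10 points, which meets the 10-point category in SAP 10.6, and there is a normal-to-low shift.

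**The case against.** The strongest reply is that the general sentence comes first and governs, and that the Period 2 sentence was meant only as a restriction, like the protocol's. That may have been the intention, but the sentence says which assessment the baseline will be, so it reads as a selection rule.

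A second reply is that the entry condition protects the gap. Much of this stands. A reader might infer that the extra weeks are when a sick subject is most likely to be seen, so that sick-visit values would commonly become baselines. The documents do not support that: those weeks are, by the entry condition, meant to be infection-free, and a sick visit within them is a case for the medical monitor. The condition does not remove an undosed visit around Day 57 or a follow-up visit.

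A reader might also infer that, if the pre-dose value is missing, the Period 2 sentence points to a post-dose value. It does so only in isolation. The sentence before it limits the period baseline to measurements before the first dose of the period, so that reading fails.

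Finally, the pre-dose value is not lost to the analysis. SAP 8.1 separately summarizes the Day 1 post-dose change in ppFEV1 from pre-dose in each period, and the data are listed. This stands, but it does not repair the baseline used for later visits in Period 2.

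**Conclusion.** The inconsistency is real, both within SAP 6.2.1 and between it and the protocol. After a 28-day extension it leaves 27 or 28 days (30 or 31 with the +3 days) in which an assessment replaces the Period 2 pre-dose value. Without an extension the gap is 0 days, or 2 to 3 if the tolerance is used.

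Its reach is narrow. It touches Period 2 only, and essentially only subjects with an extended washout and an assessment in the gap. It affects counts of ppFEV1 and FEV1 decreases, oxygen saturation shifts, laboratory changes, and ECG and vital-sign changes with their change-based thresholds. It is tempting to say that all Part A safety tables are at risk, but they are not: Period 1 is unaffected, weight, height and BMI have their own rule, and the laboratory thresholds in SAP Appendix III are absolute or relative to the normal range. Efficacy uses the study baseline.

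The documents give no count of affected subjects; the number is probably small. The size of any distortion in one subject rests on assumed values, and its direction is not fixed. This is a minor point, worth settling before unblinding so that the choice is not made afterwards.

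**What to change.** Replace the Period 2 sentence in SAP 6.2.1 with wording such as:

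*Period 2 baseline: the latest non-missing value, from a scheduled or unscheduled visit, taken after the Period 1 TE period has ended and before the first Period 2 dose.*

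This selects the pre-dose value on the Period 2 dosing day whenever it was measured, however long the washout. It follows the SAP's rule for weight, height and BMI, except that it requires a value before the dose, where that rule accepts any value up to and including the dosing day.

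It still differs from the protocol, which anchors on the last Period 1 dose and does not cap the TE period at 28 days for continuing subjects. Either record both differences in SAP section 11, or adopt the protocol's anchor and record only the cap. The choice matters when no value exists between the end of the TE period and Period 2 dosing: the protocol's anchor would let an earlier washout value, even the Day 29 visit, stand in, whereas the TE anchor would leave the baseline missing. The SAP should say which is intended.

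The cost is one sentence and one entry in section 11. No new data are needed.

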6.2.2 Treatment Emergent Period

Treatment-emergent (TE) period for Part A Treatment Period 1:

1006696
Parion Sciences Incorporated
CLEAN-PCD
SAP Version 1.0

- The Treatment-Emergent Period will correspond to the interval from the first dose date of Treatment Period 1 to 28 days after the last dose date of Treatment Period 1 or the date before the first dose date of Treatment Period 2 or the safety follow-up visit, whichever occurs earlier.

TE period for Part A Treatment Period 2:

- The treatment emergent period will correspond to the interval from the first dose date of Treatment Period 2 to 28 days after the last dose date of Treatment Period 2 or the date before the first dose date of Part B or the safety follow-up visit, whichever occurs earlier.

Treatment-Emergent Period for Part B:

- The treatment emergent period will correspond to the interval from the first dose date of study drug in Part B to 28 days after the last dose date of Part B or the safety follow-up visit, whichever occurs earlier.

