| Inhaled study drug dose in clinic     | X  |  |   |                              | X   |   |  | X   |   |   |                             |  |  |                               |  |
| Meal or snack in clinic               |  |  |   |                              |   |   |  | X   |   |   |                             |  |  |                               |  |
| Ivacaftor dose in clinic u |  |  |   |                              |   |   |  | X   |   |   |                             |  |  |                               |  |
| Dispense inhaled study drug           | X  |  |   |                              | X   |   |  | X   |   |   |                             |  |  |                               |  |
| Dispense ivacaftor                    |  |  |   |                              |   |   |  | X   |   |   |                             |  |  |                               |  |

q Urinalysis at Day 1, Day 29, Day 57, Day 85, and Day 113. Urine sodium, potassium, and creatinine analysis at Day 1, Day 15 (if a visit is planned), Day 29, Day 57, Day 71 (if a visit is planned), Day 85, Day 99 (if a visit is planned), and Day 113.

█ [Redacted]  
█ [Redacted]  
█ [Redacted]

u Ivacaftor should be administered every 12 hours (q12h) with fat-containing food. The first dose of ivacaftor in Part B will be administered on the Day 85 Visit, after completion of the Day 85 pre-dose assessments.

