### 8.1.3.2 Part B

Part B comprises Treatment Period 3 and is optional.

#### 8.1.3.2.1 Treatment Period 3

In order to continue into Treatment Period 3 the subject must sign the Part B informed consent form (ICF) or assent, as applicable. The ICF should be signed before the Day 85 Visit to allow for delivery of study drug for Treatment Period 3.

Study visits will occur on Day 85 (also the last visit of Treatment Period 2) and Day 113 to allow for a full 28 days of study drug (inhaled study drug and oral ivacaftor).

On Day 86 and Day 87, until the telephone call is no longer required by the IDMC, subjects will have a telephone call for safety purposes (e.g., inquire about AEs). If necessary, the subject may be asked to return to clinic to follow up on a new medical problem.

The first dose of both ivacaftor and inhaled study drug in Treatment Period 3 will be administered at the Day 85 Visit, after completion of the Day 85 pre-dose assessments.

If the first dose of study drug (inhaled study drug and oral ivacaftor) administered in the clinic on Day 85 is taken in the morning, the second dose will be taken that evening. The last home dose of the twice daily study regimen in Treatment Period 3 will be taken on the evening of Day 112 and no dose will be taken on Day 113.

If the first dose of study drug (inhaled study drug and oral ivacaftor) administered in the clinic on Day 85 is taken in the afternoon, a second dose will not be taken that evening. The last home dose of the twice daily study regimen in Treatment Period 3 will be taken on the morning of Day 113, at least 4 hours before the Day 113 Visit.

Subjects should only take study drug at a maximum of twice daily.

Subjects will remain in the clinic for a total of 2 to 4 hours after dosing with study drug at the Day 85 Visit until the IDMC provides approval to only require subjects to remain in clinic for 1 hour post-dosing. The duration (2 to 4 hours) each subject stays in clinic for observation will be left to the discretion of the investigator. If the IDMC does not approve reducing the observation period to 1 hour post-dosing, then subjects will continue to be observed in clinic for 2 to 4 hours during the Day 85 Visit.

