10.1 ADVERSE EVENTS

[figure not shown]
For analysis purposes, AEs will be classified as pre-treatment adverse events (AEs) or TEAEs, defined as follows:

Pre-treatment AEs are defined as any AEs that started before the initial dosing of study drug.

TEAE: any AE that increased in severity or that was newly developed during the treatment emergent period for Part A Treatment Period 1 or Part A Treatment Period 2 or Part B. An AE that starts (or increases in severity) during a specific Part A Treatment Period or Part B will be attributed to the study drug the subject was receiving during the corresponding Part A Treatment Period or Part B.

1006696
Parion Sciences Incorporated
CLEAN-PCD
SAP Version 1.0

For AEs with missing or partial start date, if there is no clear evidence that the AEs started (or increased in severity) before the first dose of Part A, the start date will be imputed to the first dosing date of Part A and the AE assigned to the treatment in Part A Treatment Period 1. For AEs with missing or partial start date, if there is no clear evidence that the AEs started (or increased in severity) before the first dose of Part B, the start date will be imputed to the first dosing date of Part B and the AE assigned to the treatment in Part B.

For the cases in which the end of treatment emergent Period 2 is on the same day as the start of treatment emergent Period for Part B, any AE starting on the same day as start of treatment emergent Period for Part B, will be assigned to the treatment in Part B.

AE summary tables for Part A and B will be presented for TEAEs only and will include the following:

[figure not shown]
- All TEAEs
- TEAEs by worst/highest relationship (includes Related, Possibly Related, Unlikely Related and Not Related)
- TEAEs by maximum severity (includes Mild, Moderate, Severe, and Life threatening)
- TEAEs leading to treatment discontinuation
- TEAEs leading to drug interruption
- Serious TEAEs
- TEAEs leading to death
- Frequently reported TEAEs

A frequently reported TEAE is defined as more than 2 subjects who have TEAE preferred term incidence for at least 1 treatment group.

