10.2 LABORATORY EVALUATIONS

The actual values and absolute changes from Part A period baseline and Part B baseline for the continuous laboratory parameters will be summarized in SI units by treatment at each scheduled visit for Part A and Part B respectively.

The number and percentage of subjects with at least 1 laboratory abnormality meeting the threshold analysis criteria during the Treatment Emergent Period for Part A and Part B will be summarized by treatment. The Thresholds Range Analyses criteria are provided in [Appendix III](#).

Results of urinalysis and serum/urine pregnancy tests will be listed in individual subject data listings only. In addition, a listing containing individual subject laboratory measurements outside the reference ranges will be provided. This listing will include data from scheduled and unscheduled time points.

Urine sodium, potassium and urine sodium to potassium ratios will be summarized by treatment.

1006696
Parion Sciences Incorporated
CLEAN-PCD
SAP Version 1.0

Serum potassium exceeding 1.1 * upper limit of normal (ULN) and/or plasma potassium exceeding 1.1 * ULN will also be summarized and listed.

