APPENDIX VI VISIT WINDOWS

The unscheduled or early withdrawal visit will be mapped to a scheduled visit for analysis using the date of collection/assessment as a basis to determine study day and then study day will be mapped to the intended visit. Table 8 and Table 9 below contain the analysis visit windows.

Table 8. Study windows

Study Period	Scheduled Visit/Day	Study Day Window	Analysis Visit
Period 1	Day 15 Visit	Day >1 - ≤ 22	Day 15
	Day 29 Visit	Day >22 - ≤ 36	Day 29
Period 2	Day 71 Visit	Period 2, Day >1 - ≤ 22	Day 15
	Day 85 Visit	Period 2, Day >22 - ≤ 36 ^a	Day 29
Period 3	Day 99 Visit	Period 3, Day >1 - ≤ 22	Day 15
	Day 113 Visit	Period 3, Day >22 - ≤ 36	Day 29

a: all assessments should happen before Part B dosing time.

For SGRQ, QOL-PCD [REDACTED] hematology, height and weight, [REDACTED] the following windows will be used:

Table 9. Study windows for Day 1 and Day 29 only

Study Period	Scheduled Visit/Day	Study Day Window	Analysis Visit
Period 1	Day 29 Visit	Day >1 - ≤ 36	Day 29
Period 2	Day 85 Visit	Period 2, Day >1 - ≤ 36 ^a	Day 29
Period 3 ^b	Day 113 Visit	Period 3, Day >1	Day 29

a: all assessments should happen before Part B dosing time.

[figure not shown]
b: visit windows for height and weight will only be applied for Period 1 and 2. Height and weight visit windows for Period 3 will be the same as table 6.

Once analysis visit windows are assigned, all visits, including scheduled visits, unscheduled visits, and early termination visits will be eligible for being flagged as the “analyzed record” within the analysis visit window. Note that the scheduled visit should match with the visit for which the visit window is defined. For example: If Day 29 visit falls in the visit window for Day 15, then Day 15 will be assigned to this visit. If no numerical measurement is available within a visit window, the measurement will be considered missing for the visit.

A subject’s individual analysis visit window could potentially contain more than one visit. In the event of multiple visits falling within an analysis visit window or in case of a

1006696
Parion Sciences Incorporated
CLEAN-PCD
SAP Version 1.0

Statistical Analysis Plan

tie, the following rules will be used in sequence to determine the “analyzed record” for the analysis visit window:

- the data closest to the scheduled day will be used.
- If there are multiple measurements with the same distance from the target day, the latest measurement will be used.

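### SAP 6.2.2 ends the Period 2 treatment-emergent period the day before Part B dosing, so Part B entrants' Day 85 pre-dose safety results drop out of the Part A threshold counts

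*SAP*

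**What the plan says.** SAP 6.2.2 closes the Period 2 TE period at the earliest of three points: "28 days after the last dose date of Treatment Period 2 or the date before the first dose date of Part B", with the follow-up visit as the third. It defines Part B TE as an "interval from the first dose date of study drug in Part B to 28 days after the last dose date of Part B" (cut short by an earlier follow-up visit). Both boundaries are calendar dates.

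Protocol 8.1.3.2.1 states that the first Part B dose of ivacaftor and of inhaled drug "will be administered at the Day 85 Visit, after completion of the Day 85 pre-dose assessments". The same section calls Day 85 the last visit of Treatment Period 2.

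SAP 10 bases all safety analyses on TE data. SAP 10.2 counts subjects with a laboratory abnormality "meeting the threshold analysis criteria during the Treatment Emergent Period for Part A and Part B". SAP 10.3 and 10.4 do the same for vital signs and ECG, and SAP 10.7 takes the lowest oxygen saturation within the TE period.

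Three places point the other way:
- Protocol 12.3.1 runs the interval for Period 2 completers "on or after first dose of Treatment Period 2 and before first dose of Part B (Treatment Period 3"), so it ends at the dose and not on the day before.
- SAP Appendix VI maps the Day 85 visit to the Period 2 analysis visit Day 29. Its footnote a requires that "all assessments should happen before Part B dosing time".
- SAP 10.1 assigns to the Part B treatment "any AE starting on the same day as start of treatment emergent Period for Part B", for the case where Period 2 TE ends on that same day. Under 6.2.2 that case cannot occur.

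SAP 11 reports no change from the protocol analysis.

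**The concern.** Day 85 serves two purposes. Its pre-dose measurements are the result of 28 days on the Period 2 inhaled treatment, and they are also the Part B baseline (SAP 6.2.1). A rule that works in whole days has to put the entire day on one side, and 6.2.2 puts it in Part B.

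Safety is a primary endpoint of both parts. A potassium, ALT or QTcF abnormality found before ivacaftor on Day 85 would be missing from the Part A count for the treatment under which it arose. If it met an absolute criterion, it could be counted under the Part B regimen instead. Whether an end-of-Period-2 result is counted would depend on the subject's later choice to enter Part B: the same result in a subject who stops after Part A is kept.

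**Working it through.** **Inputs.** Visit days and dosing times: protocol Table 3-2, 8.1.3 and 10.2.4. Boundary rules: SAP 6.2.2 and protocol 12.3.1. Planned allocation 50/50/25/25: protocol Table 8-1. Part B uptake r is not given, so a range is shown.

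**Schedule check.** 85 + 28 = 113 days and 113 + 28 = 141 days, which match the stated study durations for Part A and for Parts A + B.

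**Date rule.** End of Period 2 TE = min(last Period 2 dose + 28, first Part B dose date - 1, safety follow-up).
- Part B entrant, last Period 2 dose on Day 84 (or the morning of Day 85 for afternoon starters): min(112 or 113, 84, about 141) = Day 84. Day 85 is outside Period 2 TE. Part B TE starts on Day 85, so by date the pre-dose results are inside it.
- Non-entrant: last dose + 28 = Day 112 or 113. The follow-up call, 28 ± 7 days after the last dose, falls no earlier than Day 105. The interval therefore ends between about Day 105 and Day 113, and Day 85 is inside.

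**Scheduled post-dose Period 2 assessments left for an entrant.**

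| Measure | SAP 6.2.2 | Protocol 12.3.1 |
|---|---|---|
| Haematology | none | Day 85 |
| Chemistry, plasma potassium, ECG; Day 71 visit held | Day 71 | Days 71, 85 |
| Same; Day 71 by telephone | none | Day 85 |
| Vital signs, oximetry; Day 71 visit held | Day 57 (1 h post-dose), Day 71 | Day 57 (1 h), Days 71, 85 |
| Same; Day 71 by telephone | Day 57 (1 h post-dose) | Day 57 (1 h), Day 85 |

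**Size.** Part A plans 150 x 2 = 300 end-of-treatment assessments, of which 150 are in Period 2. With no dropout, the number lost is 150r and the share lost is 150r / 300 = 0.5r.

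| Uptake r | Lost of 300 | Share |
|---|---|---|
| 0 | 0 | 0% |
| 0.50 | 75 | 25% |
| 0.75 | 112.5 | 37.5% |
| 0.90 | 135 | 45% |
| 1.00 | 150 | 50% |

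Each treatment is given in Period 2 to half of its planned subjects (50 of 100 for each HS-containing treatment, 25 of 50 for each of the other two). With equal uptake the share lost is therefore the same in all four.

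**Effect on an incidence, upper bound.** Suppose every event is seen only at the end-of-period sample and entrants stay in the denominator. Reported incidence = p x (1 - 0.5r). For p = 10%: r = 0.5 gives 7.5%, and r = 0.9 gives 5.5%.

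**What can carry into Part B.** The Day 85 pre-dose value is the Part B baseline, so its change from that baseline is zero. It cannot meet an Appendix III criterion that requires a change. The laboratory criteria, and the absolute ECG and vital-sign criteria, can be met. SAP 6.2.2 and 10 do not exclude baseline records from TE counts.

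**The case against.** The best defence is that the SAP already handles Day 85 elsewhere. Appendix VI assigns the pre-dose record to Period 2, so the by-visit laboratory, vital-sign, ECG and oximetry summaries have a Day 85 allocation, and safety spirometry is counted by scheduled time point. Out-of-range laboratory values are listed whatever their timing. This stands, with one reservation: the opening of SAP 10, read literally, limits by-visit summaries to TE data as well. It does not protect the threshold counts or the oximetry shift, which are tied to the TE period.

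Several stronger readings are tempting, but the documents do not support them.
- A reader might infer that no post-dose safety data remain in Period 2. The one-hour vital signs and oximetry on Day 57 do remain (protocol Table 3-2, footnote l). Physical examination is listed only, and urine sodium and potassium have no Appendix III threshold, so neither has a threshold count to lose.
- A reader might infer that all the lost events reappear under ivacaftor. Only absolute criteria can carry over, and the Part B column is ivacaftor plus the same inhaled treatment.
- A reader might infer a bias between treatments. None is shown unless uptake differs by sequence.
- A reader might take 7.5% or 5.5% as an expected result. It gives no credit to Day 71 visits or unscheduled tests. It also assumes that entrants stay in the denominator, whereas SAP 13.1.5.2 by default uses subjects who have an observation.

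On adverse events, protocol 13.1.1.3 requires the date of first occurrence and not the time. Some same-day convention is therefore needed, and SAP 10.1 states one openly. An event with onset before Day 85 stays in Period 2. What remains is narrower: the rule sends an event to Part B even when the record shows that it was found at the pre-ivacaftor assessments.

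**Conclusion.** SAP 6.2.2 is wrong as written. For subjects dosed in Part B at the Day 85 visit, it removes the end-of-Period-2 results from the Part A laboratory, ECG and vital-sign threshold counts and from the oximetry shift. It also allows pre-ivacaftor abnormalities on absolute criteria to count in Part B. It contradicts protocol 12.3.1, SAP Appendix VI and the premise of SAP 10.1, with no change declared.

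The loss is up to half of the Part A end-of-treatment assessments, and a quarter at 50% uptake, under planned numbers and no dropout. The gap is complete for scheduled post-dose haematology in Period 2, and for chemistry, plasma potassium and ECG where Day 71 was a telephone call. The effect on any reported incidence is bounded by the figures above and cannot be fixed more closely, because neither uptake nor the share of Day 71 calls is documented. The primary ppFEV1 analysis uses the visit windows and is unaffected.

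**What to change.** - **SAP 6.2.2:** end Period 2 TE immediately before the date and time of the first Part B dose, and start Part B TE at that dose.
- **SAP 10.2 to 10.4 and 10.7:** state that Day 85 pre-dose assessments count for the Period 2 treatment in the threshold counts and the oximetry shift. State also that a period's own baseline record is not counted as a TE event of that period. This covers Day 1 and Day 57 as well, whose pre-dose values fall by date inside the intervals they precede.
- **Period 1:** keep the present end rule. Taking over the protocol definition throughout would extend Period 1 TE to the first Period 2 dose and so include Day 57 pre-dose. SAP 6.2.1 takes the Period 2 baseline from the first assessment after Period 1 TE, so the intended baseline would be lost. If the Period 1 rule is changed, 6.2.1 must be amended with it.
- **SAP 10.1:** assign a Day 85-onset AE to Period 2 when the record shows that it was found at or before the pre-dose assessments. Otherwise keep the existing same-day rule as the default.
- **SAP 11:** declare whatever still differs from protocol 12.3.1.

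The cost is SAP wording and one derivation rule before database lock. Appendix VI already relies on the Part B dosing time. The small downside is a blinded check of Day 85-onset AEs.
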